13.2 Sample Size/Accrual Rate

The planned sample size is 55 subjects ($50 + 10\%$ for in-evaluable / loss to follow-up = 55). Subjects who come off protocol prior to day 29 of treatment (i.e. prior to infusion of study drug) will be replaced. It is anticipated that the average site will pre-screen several subjects per month and enroll approximately 3 subjects per year.

13.3 Stratification Factors

Patients will be stratified by treating institution and delivery of primary therapy (surgery and/or radiotherapy vs no primary therapy to the prostate).

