	
changes in CTC counts (centrally assessed, optional)
 
 • To explore the feasibility of quantitative assessment of PSMA expression in CTCs and explore prognostic and predictive implications of PSMA expression in circulating tumor cells prior to therapy with Lu-J591 (centrally assessed, optional) • To assess the implications and changes with therapy of plasma markers of hemostasis, fibrinolysis, and angiogenesis in biochemically progressive castrate resistant prostate cancer (centrally assessed, optional). • To describe reasons for lack of participation in study treatment • To assess patient reported outcomes in the setting of non-metastatic CRPC and with the development of metastases
Methodology:	Subjects will be randomized in a 2:1 fashion to receive ketoconazole with 70 mCi/m ² of ¹⁷⁷ Lu-J591 or trace-labeled ¹¹¹ In-J591. Subjects will be stratified by site and method of primary therapy (surgery vs radiation). All subjects will receive ketoconazole (400 mg po TID) plus hydrocortisone (20 mg am, 10 mg pm) for 4 weeks followed by a single infusion of ¹⁷⁷ Lu-J591 or trace-labeled ¹¹¹ In-J591, then continue ketoconazole/hydrocortisone until progression/toxicity. Patients will be followed for response (biochemical), disease progression, and toxicity with the primary endpoint of time to radiographically apparent metastatic disease
Number of Patients Planned:	55
Statistical Methods	Based upon entry criteria, we expect 50% of patients to have developed metastasis at 18 months with ketoconazole + ¹¹¹ In-J591. With a sample size of 50 (2:1 randomization), the study will have $\geq 80\%$ power, with a pre-set one sided alpha of 10%, to determine an absolute difference in the 18-month metastasis-free survival (MFS) between groups of 30% (e.g., 80% vs 50%). An additional 10% will be enrolled to account for unevaluable subjects and loss to follow-up, resulting in a planned final n = 55.

TABLE OF CONTENTS

	Page
SCHEMA	iv
PROTOCOL SUMMARY	v
1. OBJECTIVES	1
1.1 Primary Objectives	1
1.2 Secondary Objectives	1
1.3 Exploratory Objectives	1
2. BACKGROUND	2
2.1 Disease	2
2.2 Investigational Agent	7
2.3 Rationale	13
2.4 Correlative Studies Background	13
3. PATIENT SELECTION	18
3.1 Inclusion Criteria	18
3.2 Exclusion Criteria	19
4. ENROLLMENT & REGISTRATION PROCEDURES	21
4.1 Enrollment Procedures	21
4.2 Central Patient Registration	22
5. TREATMENT PLAN	23
5.1 Agent Administration	23

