Unfortunately, after primary therapy with surgery or radiotherapy, some men suffer relapsed disease. In the current PSA era, the majority of these relapses are initially “biochemical” only, i.e. with a rising PSA despite no evidence of cancer on scans (5, 6), affecting approximately 50,000 or more men per year in the U.S. alone. Some of these men may be “salvaged” with appropriate therapy for local relapse (radiation for those that had surgery first, and surgery or cryotherapy for those with locally relapsed disease after radiotherapy) (6). Although there is no proven overall survival benefit in a prospective randomized trial, radiotherapy as a salvage regimen after radical prostatectomy can lead to long-term survival in selected individuals (7-10). However, most patients who receive local or regional radiotherapy with the hopes of cure after biochemical relapse following surgery subsequently suffer systemic progression. We have demonstrated J591-based therapy’s ability to successfully target known sites of disease and have positive signals of ¹⁷⁷Lu-J591’s efficacy in the advanced setting (see below). Since forms of radiotherapy have been validated in the clinically localized as well as salvage setting, “targeted radiotherapy” in the form of radioimmunotherapy is at least theoretically an attractive option with the possibility of even greater efficacy in the minimal disease (biochemical only) setting. The most studied form of radioimmunotherapy to date uses targeting of the CD20 antigen (¹³¹I tosiumomab and Y⁹⁰ ibritumomab tiuxetan) in non-Hodgkin’s lymphoma. While approved in the relapsed setting, it appears that these therapies have their greatest impact in the minimal disease setting (11-16). In addition, the decay characteristics of ¹⁷⁷Lu with its relatively short range beta emission is preferably suited for small volume, rather than bulky, disease sites.

Prostate specific membrane antigen

Prostate specific membrane antigen (PSMA) is the single, most well-established, highly restricted prostate epithelial cell membrane antigen known (17-22). The PSMA gene has been cloned, sequenced, and mapped to chromosome 11p (18, 23). Although first thought to be entirely prostate-specific (17-19), subsequent studies demonstrated that PSMA is also expressed by cells of the small intestine, proximal renal tubules and salivary glands (21). However, the level of expression in these non-prostate tissues is 100-1000-fold less than in prostate tissue (22),

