3.1.2 Biochemical progression (rising PSA) after medical or surgical castration

- Subjects who have received antiandrogens (such as bicalutamide) and have experienced PSA decline must have biochemically (PSA) progressed following discontinuation of anti-androgen therapy.
- **PSA:** An increase in PSA determined by two separate measurements taken at least one week apart and confirmed by a third, and if necessary, a fourth measurement. If the third measurement is not greater than the second measurement, then a fourth measurement must be taken; the fourth measurement must be greater than the second measurement for the patient to be eligible for enrollment in the study. Furthermore, the confirmatory PSA measurement (i.e., the third or, if applicable, fourth PSA measurement) must be ≥ 1 ng/mL with prior prostatectomy or ≥ 2 ng/mL without prostatectomy and $\geq 25\%$ above the previous nadir.

3.1.3 High risk of systemic progression defined as:

- Rising PSA as defined above and either:
 - Absolute PSA > 20 ng/mL
AND/OR
 - PSA DT < 8 months

PSA doubling time (PSA-DT) will be calculated using a linear regression model. In the model, the logarithm of PSA will be modeled as a linear function of time. The PSA-DT will be calculated as the product of $\log 2$ multiplied by the reciprocal of the slope of the regression equation, for which the logarithm is the natural log function. For standardization purposes across sites, a web-based PSA doubling time calculator developed by Memorial Sloan Kettering, is available at <http://www.mskcc.org/mskcc/html/10088.cfm>

The minimum PSA value for eligibility will be greater than or equal to 1 with prior prostatectomy or at least 2 ng/mL without prostatectomy. All PSA values of at least 0.1 ng/mL over the past 6 months must go into the equation. A minimum of 3 PSA values with a minimum of 2 weeks between assessments is required (the screening PSA may be used for the 3rd value if necessary).

- 3.1.4 No evidence of local recurrence or distant metastases within 1 month of enrollment (or following enrollment as part of screening) including:
 - Radionuclide bone scan without evidence of metastatic disease
 - In the event of an equivocal bone scan, confirmation is needed with Xray, CT scan, or MRI
 - CT or MRI of abdomen/pelvis without evidence of metastatic disease or recurrent disease in the prostate or prostate bed

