 - If no prior prostatectomy or radiation to the prostate, multiparametric MRI (mpMRI) of the prostate must have been performed and scored with PIRADS v2. The PIRADS score must be <3. (Appendix H: Summary of PIRADS V2 Scoring). mpMRI must be performed within 30 days prior to randomization.
 - Chest Xray or CT of chest without evidence of metastatic disease
 - Digital rectal exam (DRE) without clinical suspicion of recurrent/persistent prostate cancer
- 3.1.5 Age \geq 18 years.
- 3.1.6 Serum testosterone \leq 50 ng/ml
- 3.1.7 The effects of J591 on the developing human fetus at the recommended therapeutic dose are unknown. For this reason, patients capable of fathering children must agree to use an effective method of contraception for the duration of the trial.
- 3.1.8 Subjects on bisphosphonate therapy or denosumab must be on a stable dose and must have started therapy \geq 4 weeks prior to protocol therapy. Initiation of bisphosphonate therapy or denosumab is not allowed during the treatment phase.
- 3.1.9 Ability to understand and the willingness to sign a written informed consent document.

3.2 **Exclusion Criteria**

- 3.2.1 Use of red blood cell or platelet transfusions within 4 weeks of treatment
- 3.2.2 Use of hematopoietic growth factors within 4 weeks of treatment
- 3.2.3 Prior cytotoxic chemotherapy and/or radiation therapy within 4 weeks of treatment
- 3.2.4 Prior radiation therapy encompassing >25% of skeleton (see Appendix C)
- 3.2.5 Prior treatment with ⁸⁹Strontium or ¹⁵³Samarium containing compounds (e.g. Metastron®, Quadramet®)
- 3.2.6 Platelet count <150,000/mm³ or known primary qualitative platelet disorder
- 3.2.7 Absolute neutrophil count (ANC) <2,000/mm³
- 3.2.8 Hematocrit <30 percent and Hemoglobin < 10 g/dL
- 3.2.9 Abnormal coagulation profile (PT or INR, PTT > 1.3x ULN) unless on therapeutic anticoagulation – see concomitant meds section
- 3.2.10 Serum creatinine >2.5 mg/dL
- 3.2.11 AST (SGOT) >2x ULN
- 3.2.12 Bilirubin (total) >1.5x ULN; subjects with Gilbert's syndrome will be allowed if direct bilirubin is within institutional normal limits
- 3.2.13 Active serious infection
- 3.2.14 Active angina pectoris or NY Heart Association Class III-IV
- 3.2.15 ECOG Performance Status > 2
- 3.2.16 Life expectancy <12 months
- 3.2.17 History of deep vein thrombosis and/or pulmonary embolus within 1 month of study entry

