10.1 STUDY PROCEDURES: Schedule of Events

The assessments to be performed during the study are outlined below by study period, visit and day. Study assessments through Visit 9 (Day 85) will be completed within ± 3 days of the specified day for the visit, except where noted. Visits after Day 169 will be performed within ± 7 days of the scheduled visit.

Screening Period (Visit 1, Days -28 to -1) – All subjects

The procedures outlined for Visit 1 must be completed prior to the patient receiving study drug. The following procedures will be conducted at Visit 1:

- Informed Consent
- Medical History
- Concurrent medications
- Complete Physical Exam
- Vital Signs
- Demographics
- Previous therapy
 - Surgical report will include date and type of surgery +/- lymphadenectomy
 - Radiotherapy report will include modality of therapy with prescribed dose and field and dates of therapy
 - Previous hormonal therapy – drugs, doses, dates of therapy
 - Continuous vs intermittent therapy
- ECOG Performance Status
- Height, Weight
- CBC with differential and platelet count.
- PT or INR, PTT
- Electrolytes, BUN, Creatinine
- Total protein, albumin, calcium, total bilirubin, AST, ALT, LDH
- PSA
- PSA DT Calculation

- Alkaline phosphatase
- Testosterone
- Human anti-J591 antibody sample (may also be drawn C1D1 prior to initiation of study drugs)
- Urinalysis
- Archival Tissue (section 9.1.4) - Paraffin-embedded tumor blocks or 5 unstained slides with representative tumor tissue
- EKG, up to 1 month prior to treatment
- CT or MRI (abdomen-pelvis), up to 4 weeks prior to enrollment
- Bone scan, up to 4 weeks prior to enrollment
 - Any confirmatory tests to assess equivocal results of bone scan should also be completed within 4 weeks of enrollment
 - CXR, up to 4 weeks prior to enrollment (if CT chest has been performed within 4 weeks of enrollment, this procedure is waived)

Evaluations and procedures at Visit 2 (C1D1) – All subjects

Following screening procedures, eligible patients will be dosed with ketoconazole and hydrocortisone. See Section 5.1 for details on the dose and administration.

The following assessments are to be collected prior to drug administration unless otherwise noted:

- Interval medical history
- Targeted Physical Examination with vital signs
- ECOG PS
- CBC with differential and platelet count*
- Electrolytes, BUN, Creatinine*
- PSA*
- Adrenal hormone levels
- Plasma markers
- CTC's
- Adverse Events

- Concomitant medications

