13. STATISTICAL CONSIDERATIONS

13.1 Study Design/Endpoints

The study is a randomized phase 2 study with a 2:1 ratio favoring ^{177}Lu -J591, with stratification by investigational site and mode of primary therapy (radiation vs surgery). Randomization will be performed by using a series of randomized blocks of 6 within each participating site/primary therapy stratum (with a 2:1 allocation ratio). This will provide assurance that after six patients are enrolled in any given participating site/primary therapy stratum, there will be four patients assigned to the combination regimen (Group 1) and two patients assigned to the single regimen (Group 2). This procedure will allow for each site to contribute similar numbers of ^{177}Lu -J591/ketoconazole patients and ^{111}In -J591 (placebo)/ketoconazole patients within the defined participating site/primary therapy strata.

The primary endpoint is the proportion free of metastases in each group at 18 months. Ninety-five percent confidence intervals (95% CI) will be estimated for the 18-month MFS proportion in both groups via binomial proportions. The MFS proportion will also be descriptively evaluated at 12, 24, 30, and 36 months in each group.

MFS will be measured from the start of the treatment to the date of either documentation of metastatic disease or death. All treated patients will be observed for a minimum of 18 months. The 18-month MFS proportion with ketoconazole + ^{111}In -J591 has been estimated to be 50% {521 Smith, M.R. 2005}; therefore, the target 18-month MFS proportion for the combination of ketoconazole + ^{177}Lu -J591 regimen is hypothesized to be 80%. An intent to treat analysis will include all randomized subjects. However, we will also analyze subjects who received study-drug. This subset will be those subjects who met eligibility requirements, have initiated therapy, and were not removed from the study for non-compliance or patient withdrawal within the first 4 weeks, and received infusion of study drug.

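### The primary-therapy stratification factor is defined in two incompatible ways: 13.1 has no level for eligible untreated men, and 13.3 does not balance surgery against radiation

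*Combined protocol and SAP*

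**What the plan says.** Three places define the factor.

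- Synopsis, Methodology: "Subjects will be stratified by site and method of primary therapy (surgery vs radiation".
- Section 13.1: "with stratification by investigational site and mode of primary therapy (radiation vs surgery".
- Section 13.3: "Patients will be stratified by treating institution and delivery of primary therapy (surgery and/or radiotherapy vs no primary therapy to the prostate".

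The factor is used directly in allocation. Section 13.1 specifies "randomized blocks of 6 within each participating site/primary therapy stratum", at 2:1.

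Inclusion criterion 3.1.4 provides for men without local treatment: "If no prior prostatectomy or radiation to the prostate, multiparametric MRI (mpMRI) of the prostate must have been performed". The background (2.1) also foresees men with both treatments, since it lists as one salvage option "radiation for those that had surgery first".

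For the primary endpoint, 13.1 gives binomial proportions by arm at 18 months. It does not say whether the stratification factor enters the comparison.

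**The concern.** The two definitions are different partitions of the same men. Section 13.3 merges the two groups that the synopsis and 13.1 separate, and 13.1 has no level for the group that 13.3 separates. Both cannot be the single therapy factor behind the lists, so two statisticians working from this document could build different lists.

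Two things are at stake. If 13.1 governs, the rule cannot be applied to some men whom the protocol admits. If 13.3 governs, the balance between surgery and radiation stated in the synopsis and 13.1 is not delivered, and the analysis text does not make up for it.

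**Working it through.** **1. The plan's own figure.** Section 13.1 gives at least 80% power for 80% vs 50% with 34 and 17 men, one-sided 10%. The standard error is sqrt(0.80×0.20/34 + 0.50×0.50/17) = sqrt(0.00471 + 0.01471) = 0.139. Then 0.30/0.139 − 1.282 = 0.87, which is power of about 81% (81.6% with the pooled-variance formula). The figure reproduces and does not depend on the stratification factor.

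**2. Each treatment history under each definition.**

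| History | Synopsis and 13.1 | 13.3 |
|---|---|---|
| Surgery only | surgery | treated |
| Radiation only | radiation | treated |
| Both | not stated | treated |
| Neither | no level | untreated |

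**3. Men without a level under 13.1.** The documents give no therapy mix. Assuming 5-20% untreated: 0.05 × 55 = 2.75 and 0.20 × 55 = 11, so about 3 to 11 men.

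**4. Balance of surgery under 13.3.** Assume surgery in 50-70% of treated men.
- With no stratification on therapy and 37 vs 18 men, the SD of the arm difference in surgery share is sqrt[p(1−p)(1/18 + 1/37)].
- At p = 0.50 × 0.95 = 0.475 this is 0.143, and the chance of a difference above 20 points is 2[1 − Φ(0.20/0.143)], about 16%.
- At p = 0.70 × 0.95 = 0.665 the SD is 0.136 and the chance about 14%.
- Simulated allocation under 13.3 (5, 10 or 20% untreated; 10 or 16 sites; equal or unequal accrual; blocks of 4:2) gives an SD of 13-15 points. The difference exceeds 20 points in 13.1-16.7% of trials (6,000 per setting) and 12.9-18.1% (1,500 per setting). So 13.3 balances surgery no better than ignoring therapy.
- With three levels by site the corresponding ranges are 3.6-10.9% and 3.3-11.7%.

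**5. Possible effect on the estimate.** The shift is imbalance × prognostic gap. A 20-point imbalance with assumed gaps of 10, 20 and 30 points in metastasis-free proportion gives 2, 4 and 6 points, against the standard error of 13.9 points from step 1.

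An analysis simulation used 51 men, 13 equal sites, 10% untreated, surgery in 60% of treated men, 13.3 allocation and 5,000 trials per setting. In the 8-9% of trials where the surgery share was more than 20 points higher in the Lu arm, the unadjusted difference was off by about 5 points (20-point gap) or 7-9 points (30-point gap). A Mantel-Haenszel difference over three therapy levels stayed within 1 point. Over all trials:

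| Assumed gap | Power, unadjusted | Power, adjusted | Type I error, unadjusted | Type I error, adjusted |
|---|---|---|---|---|
| 0 | 79.4% | 79.1% | 10.7% | 10.4% |
| 20 points | 79.8% | 80.9% | 10.7% | 10.3% |
| 30 points | 81.3% | 84.3% | 10.9% | 10.7% |

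The Monte Carlo standard errors are sqrt(0.8×0.2/5000) = 0.6 points for power and sqrt(0.1×0.9/5000) = 0.4 points for type I error. The type I differences are therefore about the size of the noise.

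**6. Cost of adjusting: empty arms.** A level with no men in one arm gets zero Mantel-Haenszel weight. With independent 2:1 allocation, n men and untreated fraction u, the chance that the untreated level exists but has an empty arm is (1−u/3)^n + (1−2u/3)^n − 2(1−u)^n.
- n = 51, u = 0.10: 0.177 + 0.030 − 0.009 = 20%.
- n = 55, u = 0.05: 0.397 + 0.155 − 0.119 = 43%.

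Simulated 13.3 blocks give about 18-19% and 41-43%.

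**7. Cost of a three-level list.** Two levels by 10-16 sites make 20-32 nominal strata, or 55/20 = 2.75 to 55/32 = 1.7 men each. Three levels make 30-48 strata, or 1.8 to 1.1 men each. In simulation, strata containing only one arm rise from 25-56% to 45-69%, and the SD of control-arm size from 1.7-2.7 to 2.2-3.0 men.

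**The case against.** **Section 13.3 may simply be the updated text.** The title in Appendix D still refers to local therapy, while 3.1.4 now provides for untreated men. Perhaps 13.3 was revised when they became eligible and the other two places were not. That is plausible, but it is inference. If it is right, the synopsis and 13.1, which contains the randomization procedure, are the texts to correct.

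**Men with both treatments may have a level after all.** Section 2.1 separates primary therapy from later salvage. If primary means the first treatment, prostatectomy followed by salvage radiation counts as surgery. That is a reasonable reading, but the plan does not state it. Nor does 2.1 say how common this sequence is, so the number of men affected is unknown.

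**Nothing shows that the factor matters for outcome.** This stands. A reader might infer prognostic importance from the PSA floor in 3.1.3, "greater than or equal to 1 with prior prostatectomy or at least 2 ng/mL without prostatectomy". But that contrasts prostatectomy with no prostatectomy, so it groups radiation with no therapy, and an entry threshold is not evidence about metastasis.

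**The error figures are assumed and conditional.** This also stands. The therapy mix and prognostic gaps are not in the documents, the 5-9 point errors belong to a tail of 8-9% of trials, and a 2-6 point shift is under half the standard error of the primary comparison.

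**An adjusted analysis can drop men.** This is correct unless handled in advance. Section 13.1 puts all randomized subjects in the intent-to-treat analysis, and an untreated level with an empty arm would contribute nothing. The fix therefore needs a pooling rule.

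**Conclusion.** The contradiction is in current text and is real. The allocation rule in 13.1 cannot be applied as written to some eligible men. The rule in 13.3 can be applied to all of them but does not deliver the stated surgery/radiation balance, with an arm difference above 20 points in roughly 13-18% of trials under the assumed mixes.

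A reader might go further and infer that the randomization is biased, that the 18-month comparison is invalid or underpowered, or that men were in fact left unplaced. The documents support none of these. Random allocation within either set of strata is unbiased. The stated power reproduces, and sample size is not materially affected. The list actually in use is not in the documents. The case for adjusting is protection against a chance imbalance in a small trial, on a factor the sponsor itself chose. It is not correction of a demonstrated bias. This should be corrected, but it does not undermine the design.

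**What to change.** 1. Put one exhaustive, mutually exclusive definition in the synopsis, 13.1 and 13.3, stating where men with both treatments and men with neither belong. An example is prostatectomy with or without radiation, radiation without prostatectomy, and neither.
2. Align the randomization list with that text. The two-level list of 13.3 may be kept, because three levels by site thin strata that are already small. The text should then say that surgery and radiation are pooled for allocation.
3. Classify men already randomized from the screening records in 10.1, which cover prior surgery ("Surgical report will include date and type of surgery +/- lymphadenectomy") and prior radiotherapy.
4. Next to the unadjusted binomial comparison, add a therapy-adjusted 18-month risk difference, for example Mantel-Haenszel over the three levels, not crossed with site.
5. Prespecify that a level with an empty arm is pooled with a named other level, so that all randomized men stay in the intent-to-treat analysis.

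The cost is wording in three places, a check or update of the list, one extra analysis line and a pooling rule. It needs no extra patients, visits or data. The simulated power in step 5 did not include the pooling rule, so the statistician should confirm it with the rule in place.
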